**Manually tracked and administrative data utilization, and process variables.**

For Aim 3, which seeks to place Aim 1 and 2 findings in context and identify areas needing refinement for future implementation, we will capture various process and administrative data.

1. *Intervention only: MOVE!+UP* group and phone session attendance, no shows, and cancellations, including participation in the walks and reasons for non-participation in any aspect of *MOVE!+UP* sessions.
2. *Intervention only:* We will assess time and costs associated with all *MOVE!+UP* activities. Personnel time will be captured during start-up activities like initial training, and once *MOVE!+UP* is running, for one week each quarter, modeled prior research. Research and clinical personnel will enter time spent that week on *MOVE!+UP* training, recruitment, supervision, delivery, and documentation into a system developed by Liu et al. To estimate personnel costs, we will multiply hours each research and clinical personnel spent by their hourly wage rate, as recorded in the VA Personnel and Accounting Integrated Data, or imputed using Bureau of Labor Statistics data. Co-I [name] is applying these methods to analyze implementation costs in a QUERI partnered evaluation. Facilitators and research staff also provide observations and input throughout the course of the study to further assess and inform implementation= (in secure SFFX folder).
3. *For intervention only:* The following information was collected on a basic spreadsheet (see weight goal tracker: weigh-in weights; physical activity and diet quality goals and goals progress (whether meeting them fully, partially, or not); and any additional relevant information in an open-ended comments box. We also copied, scanned, and provide feedback on weekly diet and activity logs, again to be used for clinical purposes and to be evaluated as an exploratory diet quality measure. Both the activity/diet log copies, and the weekly weight/goal tracking documents were stored securely in a locked cabinet, with only a subject ID listed.
4. *For all participants:* We will capture CDW/CPRS administrative utilization data from 12 months prior to baseline through 12 months post-baseline, including *MOVE!* visits, dietitian visits, primary care, mental health group and individual psychotherapy, and psychiatry care. We also will assess prescription of psychiatric and obesogenic and leptogenic medication from VA pharmacy files. Outpatient utilization will be drawn from administrative data, classified using an algorithm developed by a study team including Co-I [name] that defines groupings of CPT codes and provider specialty codes. Inpatient care will include all cause, psychiatric, and ambulatory care-sensitive condition hospitalizations, as identified in prior studies. We also

will pull bariatric surgery from the EHR from baseline through 12 months post-enrollment to be included in a previously planned sensitivity analysis.

If the trial is positive, costs for encounters in these categories will be measured using the VA Managerial Cost Accounting (MCA) system, adjusted for inflation. We also will capture # of Veterans eligible, ineligible, contacted, recruited and retained, and psychiatric and medical conditions associated visits in the year prior to and 12 months following enrollment (pulled through administrative data).

Starting with cohort 4, we informed participants at enrollment into the study that administrative data will be pulled even if they cease participation in the study, to ensure we have sufficient power to conduct exploratory analyses examining these administrative data-based outcomes, while introducing no additional burden to study participants.

For participants from cohorts 1-3 who withdrew from the study, administrative data will be pulled up through the date of withdrawal. However, participants from cohort 2 and 3 were asked whether they were willing to allow us to pull data from the medical record through 15 months using our phone script. We documented their response in a NTF, submit it to the IRB, and document their decision in our database.

**Post-participation activities** Several activities take place following the conclusion of Veterans' study participation. First, we sent an IRB-approved closeout letter thanking Veterans for their participation in the study. Also, once the study's primary findings are published (in approximately 2025), we will send a thank you mailing to provide findings to participants. Study staff will pull participants' current mailing addresses from CPRS to send thank you letters and hard copies of the study's primary outcomes paper. Participants will not be asked to contribute any additional data or effort to the study. The purpose of that mailing will be to inform participants of our findings and thank them for their participation. We view this concluding step as essential to sharing findings with some of our most important collaborators in the research process: the study participants themselves.

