**Table 5. Quantitative Measures for RCT: Covariates, and Aim 1 and 2 Outcomes**

Domain	Measure
Baseline Covariates Associated with Weight or PTSD (will be adjusted in a weight or b PTSD analyses)	
African-American race/ethnicity a	Self-reported African-American race/ethnicity 
Aim 1: Test MOVE!+UP's Effects on Weight (Primary) and PTSD (Secondary) Outcomes	
Primary outcome: weight loss	Standardized protocol and equipment at baseline and 6 months. Will also explore 12-month weight loss in secondary analyses.
Secondary outcome: PTSD symptoms	PTSD Checklist for DSM-5  PTSD symptomology will be recorded at baseline, 6 months, and 12 months.
Aim 2: Exploratory Changes on Treatment Targets from Baseline to 6 months	
Diet quality and eating habits	Starting the Conversation  and PACE eating habits measure
Night eating	Night Eating Questionnaire 
Emotional eating	Emotional Overeating Questionnaire 
Binge eating with purging vs binge eating without purging vs no binge eating	PHQ-15  modified to reflect DSM-5 changes plus items from PACE eating habits
Two outcomes: Average physical activity (light, moderate, and vigorous; moderate and vigorous)	Actigraph accelerometers, gold standard 
Social support	Helpful and unhelpful behaviors from others for activity/diet 
Insomnia severity	Insomnia Severity Index 
Depression symptoms	PHQ-8 
Internalized Weight Bias	Modified Weight Bias Internalization Scale

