**Eligibility assessment (15-30 minutes; see ALT Eligibility Measures).**

The follow-up eligibility assessment was conducted virtually, ideally by VVC, at a time that allowed study materials to have been mailed to the participant. The various components of the assessment visit can be completed on different dates as needed (as long as all components are completed within the acceptable assessment visit window) to best accommodate Veterans. Ideally, all components would be completed on the same day during the same VVC visit.

Prior to the visit, study staff confirmed receipt of mailed materials and the study scale and would troubleshoot any issues with VVC connection. Should VVC be having issues, staff would send the participant a link, via one-way text or email to the participant, to another approved video conferencing modality from which they could join the assessment visit (see Text Scripts).

Study participants were asked to weigh themselves with the study-provided scale to confirm they meet the eligibility criteria for the study (overweight/obese status; BMI of at least 25). Height for BMI calculation was based on CPRS-based information.

They also completed a current assessment of PTSD symptoms, administered by study staff. Current PTSD was confirmed during this visit as indicated by endorsing at least one lifetime traumatic event on the Life Events Checklist for DSM-5 (LEC-5) and based on their score on the PTSD Checklist for DSM-5 (PCL-5). A provisional PTSD diagnosis can be made by following the DSM-5 diagnostic rule, which requires at least moderate severity endorsement (a score of at least 2) on the following: 1 B item (questions 1-5), 1 C item (questions 6-7), 2 D items (questions 8-14), and 2 E items (questions 15-20). In addition, to meet PTSD diagnosis criteria, the individual must obtain a score of  $\geq 33$  on the PCL-5. As long as they continue to meet those inclusion criteria, they may be officially enrolled in the study and designated for randomization.

Respondents who do not meet eligibility criteria were offered a resource list (see Mental Health Resources Handout), and given *MOVE!* contact information and told to follow-up with their primary care provider or mental health treatment coordinator for mental health treatment or other care coordination needs.

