**Follow-up assessments (30-60 minutes)** The 16-week satisfaction questionnaire tailored for *MOVE!+UP* and *MOVE!*, was mailed to be completed on hard copy, or emailed with a personalized Qualtrics URL link to be completed electronically, to participants at approximately 15 weeks so they could complete and/or return it in a postage-paid, pre-addressed envelope at approximately 16 weeks. If the survey was not received, staff contacted the subjects via phone to obtain the 16-week data. Participants received follow-up reminder letters, emails, or phone calls if the 16-week assessment had not been completed. If subjects did not return the measure via mail or complete the measure via the emailed personal link, they had the option to complete the assessment via phone. The measure assesses 30 *MOVE!+UP* content and structure features with a Likert satisfaction scale, with space for Veterans to suggest changes for each. We modified that measure to remove the specific *MOVE!+UP* domains to assess *MOVE!* satisfaction among control participants. We sent emails to individual participants only one email at a time (rather than blind carbon copy) to avoid disclosing the email addresses of other consented subjects.

**The 6-month assessments** mirror the baseline assessment procedures. The various components of the follow-up assessment visits could be completed on different dates as needed (as long as all components are completed within the acceptable assessment visit window) to best accommodate Veterans. Ideally, all components would be completed on the same day during the same VVC visit. Ideally the subject would show their study issue scale readout to staff during the VVC session. If this is not possible, they may take a photo of the scale reading with their cell phone and text it to a staff member's GFE iPhone. This allows for the message to be encrypted. Staff do not text the Veteran back. This will only be done in the rare circumstance that the scale cannot be visualized.

**12-month follow-up assessment (15-30 minutes).** At the final assessment visit at 12 months, all participants have a final weight measurement taken. PTSD symptomology, non-VA utilization, Adverse Events, and pregnancy will also be recorded at this time. All participants will be thanked for their participation in the study. This visit takes place

via VVC (or other approved video conferencing modality should VVC not be working).

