**Table 6. Curriculum for *MOVE!+UP* Group Sessions**

Information was recorded in CPRS using standard procedures because these are clinical visits, likewise for *MOVE!* visits for the control condition.

1) *MOVE!+UP* sessions were offered by VVC and over the telephone using a backup conference line for those who may prefer to dial in and do not want to or cannot access VVC, dietician visits will be held by phone or VVC, and the community walk will be done individually during *MOVE!+UP* sessions in Veterans' own communities. In the highly unlikely case where VVC was not working, we had approval to switch to another VA-approved modality as listed in the Telehealth memorandum, titled "Use of Video Communication Technology Under COVID-19 (VIEWS 02576895)" and dated March 19, 2020.

2) Minor modifications were made to the facilitator and participant manual (see ALT Session 1 Facilitator Manual and ALT Participant Manual) from that used during the pilot to reflect information relevant to VVC delivery and recommendations appropriate during the pandemic and social distancing recommendations. Perhaps the biggest change is removing the family/friends invitation session so that it remains focused on social support but non-participants won't join (since that adds another layer of complexity for ensuring confidentiality). This is unlikely to have a major impact given no family or friends attended that session during the *MOVE!+UP* pilot.

3) We relied on phone, secure messaging, and VA's BHL Touch program for sharing clinical datapoints back and forth between facilitators and Veterans in *MOVE!+UP*, including weekly weighing, PTSD symptom assessments, diet/activity logging, photos of food labels and walking routes, and general support. Veterans were also given the option of sharing information like their weight during the group, just as is done in standard *MOVE!*. We attempted to set all study participants up with secure messaging after study enrollment to facilitate this important data sharing.

4) During each session, instead of the 40-minute facilitator-led group walk around the VA campus that was done during the pilot, participants were asked to walk in their own communities. Before the first session, they were asked to conduct walking safety audits in their community to ensure they have a safe

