## 5.6.b. Data Analysis

**Power and Sample Size Calculations.** This study is powered on weight change at six months, comparing intervention and control conditions. We used formulas specified by Friedman et al. for use in clustered randomized controlled designs. Sample size was calculated for continuous outcomes and inflated to account for clustered randomization, using the inflation factor  $1 + (m - 1)\rho$  for cluster size  $m$  and intraclass correlation  $\rho$ , and attrition. Based on outcomes in prior weight loss trials, **we expect those in *MOVE!+UP* to lose 12 pounds on average, which would likely correspond to clinically meaningful weight loss (5% of baseline weight).** The specified expected weight loss is plausible, given *MOVE!+UP* pilot participants lost an average of 14 pounds, corresponding to 6% of baseline weight. We expect those in the control condition to achieve weight loss of 3.6 pounds on average consistent with Veterans with PTSD who participate in *MOVE!*, according to administrative data.

In the power calculation, the standard deviation of the outcome was assumed to be 13 based on previous findings. We calculated this value based on the marginal SD of 50 for baseline weight observed among Veterans with PTSD in *MOVE!*, between baseline and 6-month weight observed in the *MOVE!+UP* pilot (comparable to other weight loss effectiveness trials). Comparing these outcomes, an 8.4 pound difference in weight lost corresponds to prior behavioral weight loss trials and would yield a medium Cohen's  $d$  effect size of 0.65.

Table 7 displays the sample size required for varying cluster sizes *m* and intraclass correlation coefficients  $\rho$  assuming 90% power. The sample size of N=164 total Veterans (82 Veterans per treatment arm) chosen for this study assumes an ICC of 0.03, cluster size of 8 Veterans per randomized group, 90% power, a two-sided  $\alpha$  of 0.05, and a 6-month attrition rate of 25%, similar to MOVE!+UP pilot’s overall retention and a meta-analysis of missing data in weight loss RCTs. We will also be powered to detect a meaningful change in PTSD symptoms in the intervention condition at six months, aligned with the average PTSD symptom reduction of 18 (SD=12) observed among MOVE!+UP pilot cohort 5 participants and assuming a 9-point clinically meaningful reduction in the control condition.

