If a participant decided to withdraw, or if they were terminated from the study, a person from the study team may need to meet with them to discuss the necessary steps that they may need to take to end Veteran participation in the study. Veterans were also reminded that If they decided to withdraw from the study, no new information would be collected from them (aside from prospective CDW data, noted in the consent as described above); however, data already collected will continue to be part of the analyses.

b. VA Employees (Aim 3)

VA staff participants will be assured that they can, at any time, refuse to answer any question, and at any time elect to withdraw from the study. They also will be assured that their participation or lack thereof will not be reported to their supervisor or peers nor will it have any impact on their work environment and that they are free to participate in the presence of union representation.

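### About a quarter of 6-month weights would be imputed with no follow-up weight in the model, although the planned record pull could supply dated clinic weights as an auxiliary variable

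*Combined protocol and SAP*

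**What the plan says.** Table 5 defines the primary outcome measurement as "Standardized protocol and equipment at baseline and 6 months". Under Eligibility assessment in Section 5.5, "Study participants were asked to weigh themselves with the study-provided scale". The 6-month visit follows the baseline procedure: "Ideally the subject would show their study issue scale readout to staff during the VVC session". The only fallback stated is that "they may take a photo of the scale reading with their cell phone", which is still the same scale.

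Under the heading on manually tracked and administrative data in Section 5.5, the plan says "We will capture CDW/CPRS administrative utilization data from 12 months prior to baseline through 12 months post-baseline". The items then listed are visits by type, psychiatric and weight-affecting medications, hospitalizations, bariatric surgery and visits for medical and psychiatric conditions. Weights are not among them. From cohort 4 onward, participants were told that the pull continues if they stop taking part. Section 5.7 agrees: after withdrawal, "no new information would be collected from them (aside from prospective CDW data, noted in the consent as described above". For cohorts 1-3 the pull stops at withdrawal, although cohorts 2 and 3 were asked whether it could run to 15 months.

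Section 5.6.b assumes 25% attrition at 6 months and imputes missing outcomes by chained equations. The listed variables are 6-month weight itself, baseline weight, African-American race, employment, education, age, gender and two medication indicators. The same section uses the EHR to fill in missing race, and Section 5.5 takes height from CPRS. The planned control-arm loss of 3.6 lb is described as "consistent with Veterans with PTSD who participate in *MOVE!*, according to administrative data". Sessions in both arms are charted (Section 5.6.a): "Information was recorded in CPRS using standard procedures because these are clinical visits".

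**The concern.** Anyone who misses the 6-month weighing enters the primary analysis with a value predicted from characteristics that say little about how their weight moved after randomization. If leavers did worse than stayers with the same baseline profile, and more so in one arm, the imputation carries the stayers' result over to the leavers and the treatment difference is biased.

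The missing-data sensitivity analysis in the statistical models table does not close this gap. It adds the auxiliary variables, plus any that look related to missingness, but names no follow-up weight.

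A weight recorded in the chart near month 6 would be direct evidence on some of these people. The trial is already extracting their records over the right period.

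**Working it through.** **1. The plan's own figure.** Inputs from Section 5.6.b and Table 7: difference 8.4 lb, SD 13 lb, two-sided alpha 0.05, power 90%, ICC 0.03, cluster size 8, attrition 25%.

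- Per arm before inflation: 2 x (13 x (1.960 + 1.282) / 8.4)^2 = 50.33
- Design effect: 1 + (8 - 1) x 0.03 = 1.21
- Per arm: 50.33 x 1.21 / 0.75 = 81.2, rounded up to 82, so 164 in total.

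The stated 164 reproduces.

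**2. Outcomes expected missing.** 0.25 x 164 = 41. For the 174 randomized (Abstract, Research Design), 0.25 x 174 = 43.5, about 44.

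**3. Power or bias?** With 25% missing, the effective number per arm is 82 x 0.75 / 1.21 = 50.8 for N = 164, which gives power of 90.3%. For N = 174 it is 87 x 0.75 / 1.21 = 53.9, which gives 91.9%. Power is covered, so what remains is bias.

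**4. Size of the bias.** Suppose 25% are missing in each arm, MOVE!+UP leavers lose s lb less than their imputed values imply, and control leavers lose c lb less. The overstatement is 0.25 x (s - c). The documents give neither s nor c, so these are assumptions:

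| s (lb), with c = 0 | Overstatement (lb) |
|---|---|
| 2 | 0.50 |
| 4 | 1.00 |
| 5 | 1.25 |
| 8.4 | 2.10 |

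If c = s, the bias is zero.

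**5. What a clinic weight would recover.** Let a share k of leavers have a clinic weight near month 6, and let its change from baseline correlate r with the study-scale change. Imputation on it recovers about r^2 of the shift in those leavers, so the remaining bias is about 1.25 x (1 - k x r^2) for s = 5, c = 0. Both k and r are assumed.

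| k | r = 0.7 | r = 0.9 |
|---|---|---|
| 30% | 1.25 x (1 - 0.147) = 1.07 | 1.25 x (1 - 0.243) = 0.95 |
| 60% | 1.25 x (1 - 0.294) = 0.88 | 1.25 x (1 - 0.486) = 0.64 |
| 80% | 1.25 x (1 - 0.392) = 0.76 | 1.25 x (1 - 0.648) = 0.44 |

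A simulation with 87 per arm and SD 13 agrees to within about 0.05 lb. In it the standard error falls by roughly 2-8%.

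**6. If leavers have fewer clinic weights.** Halving their coverage from 60% to 30% leaves 1.07-0.95 lb (first row above). Halving it from 80% to 40% leaves 1.25 x (1 - 0.196) = 1.00 to 1.25 x (1 - 0.324) = 0.85 lb.

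**The case against.** The strongest reply is that the benefit is modest and unproven. At 60% coverage and r = 0.7 the auxiliary removes 1.25 - 0.88 = 0.37 lb, about 4% of 8.4 lb. At 80% and r = 0.9 it removes 0.81 lb, about 10%. Charting of sessions does not show that weights are recorded, and people who leave stop attending. Sessions ran by video or phone, so any weight charted there would be the participant's own home reading. Sixteen weekly sessions last 112 days. If they begin at enrollment (the lag is not stated), they end before a window of 60 days either side of month 6 opens, at about day 183 - 60 = 123. The administrative data behind the 3.6 lb describe an earlier MOVE! population and say nothing about coverage here. All of this stands. It limits the gain but does not remove the reason to look.

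Four stronger readings are tempting, and the documents do not support them:

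- *That nothing in the data could reveal selective loss.* MOVE!+UP weigh-ins and attendance are tracked, some participants will have a 12-month study weight, and missingness is to be described by arm and against auxiliary variables. However, neither the weigh-ins nor the 12-month weight is in the listed 6-month imputation, and the weigh-ins exist in one arm only.
- *That those missing at 6 months are usually missing at 12.* No passage says so.
- *That clinic weights are excluded.* They are unlisted: the list in Section 5.5 is illustrative, and Section 8.1 mentions further unnamed variables to be pulled for Aim 1.
- *That the sample size is wrong.* It reproduces and allows for the attrition.

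**Conclusion.** The point holds as a worthwhile, low-cost improvement. The endpoint weight has a single source, the listed extraction contains no other weight, and about 44 of 174 primary outcomes would be imputed without any follow-up weight in the model. The illustrative bias of 1.25 lb depends on an assumed 5 lb shortfall confined to MOVE!+UP leavers. It would shrink or vanish if control leavers behaved similarly, and would change sign if they did worse. The remedy lowers this bias but does not eliminate it. How far depends on coverage among leavers and on the correlation with the study-scale change, and the documents give neither.

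**What to change.** Before outcome analysis:

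- Add clinic weights with their dates to the Section 5.5 extraction for both arms.
- Take the weight nearest month 6 within a fixed window, by the same rule in each arm, and add it to the imputation table as an auxiliary for 6-month weight. Do the same at month 12. The study-scale weight stays the endpoint.
- Report clinic-weight coverage by arm and by whether the study weight is missing, so that readers can judge how much was recovered.
- Keep the one-arm MOVE!+UP weigh-ins out of this auxiliary. They can be used descriptively, to see whether leavers were losing less before they left.
- Stay within the cohort 1-3 withdrawal limits. From cohort 4, the stated reason for pulling data after participation ends was to support exploratory analyses, so confirm that the consent wording allows withdrawn participants' weights to inform the primary imputation.

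The cost is one dated field in a pull already planned, one row in the imputation table, an SAP amendment (Section 5.6.b requires primary missing-data methods to be pre-specified) and possibly an IRB note. The drawback is that clinic weights are noisier and incomplete, and coverage may differ by arm. That is why they should serve only as an auxiliary.
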